1.2 SCHEMA

Figure 1: Study Flow Chart

Screening

- Obtain informed consent
- •Assess inclusion/exclusion criteria
- •Capture baseline demographics, medical history and concomitant medications
- Collect clinical assessments (height, weight, previous X-Ray interpetation if available)

Enrollment

- •Affirmation of informed consent and enrollment (Only if screening visit is independent of procedure visit)
- •One run-in subject per operator
- •Enroll Fifty (50) Patients

Procedure (within 2-days of screening)

- •Collect pre-procedure vital signs
- Place NasoEnteral Tube using NUTRIPLACE System
- Collect procedure information (including number of tube replacement events)
- •Confirm placement via X-Ray (within 5 hours)
- •Assess for adverse events and device related side effects

Follow-up (20-48 hours post procedure)

- Collect vital signs
- •Confirm tube location using NUTRIPLACE System and X-Ray
- •Collect information regarding tube migration and reposition
- •Assess for adverse events or device related side effects

Study Exit

SCHEDULE OF ACTIVITIES (SOA) 1.3

The study schedule for this evaluation is presented below in **Table 1**.

Table 1: Study Schedule

Procedures, Evaluations and	Study Visits			
Tests	Screening	Procedure (Within 2 days of Screening Visit)	Follow-up (20-48 hours after Procedure Visit)	
Informed Consent	Х	X ³		
Inclusion/Exclusion Criteria	Х			
Demographics	Х			
Medical History (Acute and Past)	Х			
Concomitant Medications ⁴	Х			
Examinations				
Targeted Physical Exam	Х			
Vital Signs		Х	Х	
Nutriseal [™] nasoenteral tube		v		
Placement		^		
Confirm Anatomical Location				
NUTRIPLACE System			v	
Abdominal and/ or thoracic X-		Y ⁶	X	
ray⁵		^	^	
Adverse Events		Х	Х	

³ Affirmation of informed consent is only required if procedure visit is independent of screening visit.

 ⁴ Limited to sedatives/any medication with sedative effect, anticoagulants and prokinetic agents.
 ⁵ Additional X-Rays may be taken if clinically indicated.

⁶ Within five hours of placement.

2 INTRODUCTION

2.1 STUDY RATIONALE

This clinical study is designed to affirm the utility of the NUTRIPLACE System during placement of the Nutriseal nasoenteral feeding tubes.

2.2 BACKGROUND

Enteral nutrition is the preferred route for the provision of nutritional support in most critical ill patients with functional gastrointestinal tract. The nasoenteric tube (NET) are easily placed at the bedside. Patients that most commonly require a NET are in the surgical, intensive care, neonatal and pediatric settings^{1,2}. Enteral tube feeding is thought to preserve the integrity of the gut mucosa, and to reduce infectious complications. Achieving early enteral nutrition (EN) in critically ill patients is associated with fewer major complications, reduced mortality and length of hospital stay, and significant cost savings^{3,4,5,6,7}.

It is estimated that approximately 1.2 million feeding tubes are placed blindly each year in the United States alone^{2,8,9,10,11}. Despite the obvious advantages of the enteral tube feeding, inadvertent placement of NET into the airway is relatively common and can result in significant pulmonary injury including pneumothorax and pneumonia. Airway misplacement occurs in 1.2–4 % of blind NET insertions, with 0.2 to 1.2% of all the feeding tube placements cause pulmonary complications to patients^{3,12,13,14,15,9}.

The gold standard for detecting inadvertent placement of a feeding tube in the lungs is radiography. However, because of its cost, possible delay of feedings while waiting for radiography, and risk for radiation exposure, clinicians continue to seek for alternative methods to confirm correct placement^{3,16}.

All the above mentioned, emphasizes the fact that safe and effective delivery of nasoenteral tube feedings requires assurance that the feeding tube tip is in a proper position¹⁷.

The NUTRIPLACE System is an electromagnetic tracking system which tracks the path of the feeding tube during placement. The System utilizes an ElectroMagnetic (EM) sensor in the NET's distal tip and a field generator as well as plate sensor (patient angle) and reference sensor (provides horizontal scaling of the body contour of the patient) and a Stylus which marks two anatomical landmarks (Xiphoid Process and Suprasternal Notch).

The benefit of the system when NET is misdirected into the pulmonary system is a real-time visual tracing, which may prompt users to withdraw the tube and reinsert it.

2.3 RISK/BENEFIT ASSESSMENT

2.3.1 KNOWN POTENTIAL RISKS

Risks associated with the placement and use of nasoenteral tubes include the following:

- Placement in the lungs resulting in:
 - o pneumothorax
 - pneumonia and sepsis
- Irritation and coughing during placement
- Damage to nasal ciliary epithelium leading to infection and/or sinusitis following long-term presence of an nasoenteral tube
- Perforation of the esophagus in patients with esophageal varicies, ulcers, or history of cancer or neoplasms
- Perforation of the base of the skull in patients with deformities of the skull base and/or sinus cavity
- Reflux of stomach contents into the esophagus leading to aspiration
- Parotitis
- Minor bleeding during tube placement

2.3.2 KNOWN POTENTIAL BENEFITS

Potential benefits provided by the NUTRIPLACE System include improved placement accuracy for enteral feeding tubes, shorten time to confirm tube position, earlier enteral nutrition, immediate detection of tube misplacement and therefore reduced likelihood of incorrect tube placement, feeding into lungs and pneumothorax. The use of enteral feeding is intended for situations where such means are necessary to potentially save the patient's life.

2.3.3 ASSESSMENT OF POTENTIAL RISKS AND BENEFITS

Taking into consideration all risks identified during analysis, and the benefits the NUTRIPLACE System provides to the patient, it has been determined to be an acceptable residual risk when weighed against the intended performance benefits.

3 OBJECTIVES AND ENDPOINTS

OBJECTIVES	ENDPOINTS	JUSTIFICATION FOR ENDPOINTS
Primary		
The objective of this study is to assess the safety of the NUTRIPLACE System as an adjunct to current practices for placement of nasoenteral feeding tubes.	Procedure success: NET tube can be placed in the correct anatomical position without occurrence of guidance-related adverse events.	This endpoint will support the performance of the NUTRIPLACE System guidance.
Secondary		
There are	e no secondary objectives for this trial	
Tertiary/Exploratory		
Procedure Metrics	Number of placement attempts per patient. Tube migration.	
Safety	Adverse Events	

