4 STUDY DESIGN

4.1 OVERALL DESIGN

This is a single center, non-randomized feasibility clinical evaluation that is designed to affirm the safety of the NUTRIPLACE System guidance during the placement of the Nutriseal nasoenteral feeding tubes. Data collected during this trial is designed to ensure that NUTRIPLACE System can be used to successfully place Nutriseal NETs in the desired location without guidance-related adverse events.

This study will be an in-hospital study which will follow enrolled subjects for an acute period of up to 48 hours post-placement.

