A full description of the System and its use is provided in the Investigator's Brochure (Attachment 1) the NUTRIPLACE System User Manual and the NasoEnteral Tube Instructions for Use (Attachment 2). The NUTRIPLACE System will be used on enrolled subjects following the documented methods and in consideration for the investigational sites standard of care regarding the placement of nasoenteral feeding tubes.

The study of the NUTRIPLACE System is considered a non-significant risk study of an investigational medical device. The rationale supporting the non-significant risk status is included in the NSR Letter (Attachment 3).

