9 STATISTICAL CONSIDERATIONS

9.1 STATISTICAL HYPOTHESES

There is no formal statistical hypothesis for the primary endpoint of this feasibility trial. The primary endpoint is defined as procedure success, e.g., NET tube can be placed in the correct anatomical position without occurrence of guidance-related adverse events.

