9.2 SAMPLE SIZE DETERMINATION

This feasibility trial will include fifty (50) patients completing the Procedure Visit (NasoEnteral Tube placement) and five operators. Each operator must complete training on one run-in subject prior to participating in this study. Patients or patients' LAR who chose not to participate after informed consent but prior to procedure, and patients who because of system malfunction or because of undiscovered or unreported physical reasons (e.g. deteriorating health, anatomical anomalies, mechanical obstruction, etc.) cannot complete the Procedure Visit (NasoEnteral Tube placement) will be considered Screen Failures, not be considered in the total patient count, but will be reported in the ITT dataset as defined below. If less than 45 patients will complete the Follow-up Visit (confirmation of tube tip anatomical location), an enrollment of another 5 patients will be considered.

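### The primary endpoint does not require that the System guided the successful placement, and no rule says how to score a tube placed correctly after guidance was lost or abandoned.

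*Combined protocol and SAP*

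**What the plan says.** The endpoint appears in the Synopsis (1.1), Section 3 and Section 9.1 in nearly the same words. Section 3 gives it as "NET tube can be placed in the correct anatomical position without occurrence of guidance-related adverse events". Section 9.1 repeats it: "The primary endpoint is defined as procedure success, e.g., NET tube can be placed in the correct anatomical position". Section 3 justifies the endpoint as support for the performance of the guidance. Section 4.1 states the aim as showing that the "NUTRIPLACE System can be used to successfully place Nutriseal NETs in the desired location without guidance-related adverse events".

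On conduct, the Procedure box of the flow chart (1.2) has the tube placed with the NUTRIPLACE System. Section 6.1 says that the System will be used on enrolled subjects by the documented methods and "in consideration for the investigational sites standard of care regarding the placement of nasoenteral feeding tubes". The Synopsis describes the System as an adjunct to current practice.

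On counting, Section 9.2 states: "This feasibility trial will include fifty (50) patients completing the Procedure Visit (NasoEnteral Tube placement) and five operators". Malfunction is covered only by the clause on "patients who because of system malfunction or because of undiscovered or unreported physical reasons" who, as a result, "cannot complete the Procedure Visit (NasoEnteral Tube placement) will be considered Screen Failures". These patients are left out of the 50 but are reported in the ITT dataset. Section 9.4 calculates procedure success in every population listed in 9.3.

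**The concern.** The aim concerns what the System can do, while the endpoint asks only where the tube ended up and whether a guidance-related adverse event occurred. The System is an adjunct, and the protocol itself foresees malfunction. It is therefore a foreseeable course that tracking is lost, or the display abandoned, and the operator finishes by usual technique. The endpoint has no condition that separates this patient from one guided all the way.

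The other listed measures do not clearly close the gap. The X-ray shows position, not how the tube got there. Sections 3 and 8.1 name attempts, replacement, repositioning and migration, none of which states whether a pass was guided. The guidance categories in 8.2.3.2 apply only to adverse events already judged at least potentially device-related, so a guidance failure without harm is not classified. The Clinical Events Committee adjudicates adverse events.

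With no hypothesis, comparator or secondary objective, this proportion is the study's main result on guidance. What is at stake is whether it describes guided placement or placement by any means.

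**Working it through.** **Step 1. Follow one patient through the text.** Guidance is lost or abandoned, the tube is then placed in the correct position, and no guidance-related adverse event occurs.

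- *Endpoint (1.1, 3, 9.1).* Correct position: met. No guidance-related event: met. Literal result: success.
- *Section 9.2, reading A: completing the Procedure Visit means that the tube was placed.* The parenthesis in 9.2 and the placement row of the schedule (1.3) support this. The patient is one of the 50 and a success.
- *Section 9.2, reading B: completing the visit means guided placement.* The flow chart and 6.1 support this, as does the naming of malfunction as a reason for not completing. After a malfunction the patient is a Screen Failure, outside the 50 but reported in ITT. The literal endpoint still scores a correctly placed tube as a success there. Guidance abandoned without a malfunction is not named in the clause.
- *Per-Protocol (9.3).* If the event is logged as a deviation, the patient leaves this dataset. The documents do not say that it is one.

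So the patient is a success or is removed. No dataset clearly scores a failure.

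**Step 2. Inputs for the size.**

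- N = 50 (9.2). The Synopsis says it has no statistical basis, and 9.1 states no hypothesis, so there is no sample-size calculation to reproduce.
- k = number of unguided completions among the 50. The documents do not give it; k = 0 to 5 is an assumption.
- For illustration, all 50 tubes are correctly placed with no guidance-related adverse event.

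**Step 3. Formulas.** Change per case = 1/50 = 2.0 points. Rate if unguided completions are not successes = (50 − k)/50. Exact (Clopper-Pearson) 95% limits for x of n: lower = Beta(0.025; x, n − x + 1) quantile, upper = Beta(0.975; x + 1, n − x) quantile. When x = n, the lower limit is 0.025^(1/n) and the upper is 100%; for n = 50, 0.025^(1/50) = 92.9%.

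**Step 4. Results.**

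| k (assumed) | Literal endpoint, reading A | Unguided scored as not a success |
|---|---|---|
| 0 | 50/50 = 100% (92.9 to 100) | 50/50 = 100% (92.9 to 100) |
| 1 | 50/50 = 100% (92.9 to 100) | 49/50 = 98% (89.4 to 99.9) |
| 2 | 50/50 = 100% (92.9 to 100) | 48/50 = 96% (86.3 to 99.5) |
| 3 | 50/50 = 100% (92.9 to 100) | 47/50 = 94% (83.5 to 98.7) |
| 5 | 50/50 = 100% (92.9 to 100) | 45/50 = 90% (78.2 to 96.7) |

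Under reading B, removing 5 such patients leaves 45/45 = 100% (92.1 to 100). If they are replaced to restore 50 completers, the figure is again 50/50. Removal hides the cases as fully as counting them as successes does.

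**The case against.** The strongest reply is that the protocol already requires the System. The flow chart has the tube placed with it, and 6.1 says that it will be used on enrolled subjects. Section 9.2 points the same way: if any placement counted, a guidance malfunction would seldom stop an operator from completing the visit, so naming malfunction there makes most sense if completion means guided placement. This stands against a stronger claim that a reader might infer, namely that completing the visit does not depend on the System and that such a patient certainly counts as one of the 50 and as a success. The text allows both readings, so *could count* is as far as it goes. But the flow chart and 6.1 describe intended conduct, not scoring, and starting with the System satisfies both even if tracking is then lost.

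Four further points deserve weight.

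- Section 10.1.9 treats any noncompliance with the protocol as a deviation to be recorded on the CRF. An unguided finish might be logged, and the contrast between ITT and Per-Protocol might then expose it. This helps only if the site regards it as a deviation, and it removes the patient rather than scoring a failure.
- Harm after lost tracking could still be classed as guidance-related, because 8.2.3.2 includes events from insufficient information. True, but this covers only cases with harm.
- A reader might infer that guidance status is not recorded anywhere. The documents do not show that: the flow chart's list of procedure information is not exhaustive, 6.1 mentions a printed placement report and screenshots, and the CRF and user manual are not available here.
- The blind airway-misplacement rate of 1.2 to 4% in Section 2.2 might be taken to show that unguided finishes nearly always succeed. It concerns the airway only, not failure to reach the correct position, and is not used here.

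**Conclusion.** The point holds as an undefined scoring rule in the primary endpoint. The stated definition, followed literally, would credit a guidance failure as a success whenever the tube still reaches the correct position. The alternative reading of 9.2 takes a malfunction case out of the 50. Neither clearly records a failure, although the endpoint is meant to support guidance performance.

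The size is 2 points per case. For an assumed 0 to 5 cases, the rate reads 100% (92.9 to 100) where it would otherwise lie between 100% and 90% (78.2 to 96.7 at 5 cases). It would be wrong to infer that the trial overstates success by 10 points. The documents give no count, zero is possible, and no success threshold is set, so no prespecified decision turns on the difference. No figure in the documents is wrong on this point.

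**What to change.** - **Endpoint (1.1, 3 and 9.1).** Define success as correct position, confirmed by X-ray, reached on a System-guided placement without a guidance-related adverse event.
- **CRF.** Make sure that one item records whether guidance was used to final position, lost or abandoned, with the reason. If this is not captured at the time, it may not be recoverable.
- **Scoring (9.4).** Score lost or abandoned guidance as not a success, both in the 50 and in ITT, and list these cases.
- **Section 9.2, with the matching text in 1.1 and 5.4.** Score system malfunctions as non-successes whether or not the tube was then placed, and do not remove them as Screen Failures. Define the count of 50 to include them. Without this change, a malfunction that prevents placement would be treated more leniently than one followed by an unguided success.

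The cost is one sentence in the endpoint, one CRF field and an aligned counting rule. The reported success rate may be slightly lower. The change concerns measurement and scoring only; it proposes no rule for clinical management after a malfunction.

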4 STUDY DESIGN

4.1 OVERALL DESIGN

This is a single center, non-randomized feasibility clinical evaluation that is designed to affirm the safety of the NUTRIPLACE System guidance during the placement of the Nutriseal nasoenteral feeding tubes. Data collected during this trial is designed to ensure that NUTRIPLACE System can be used to successfully place Nutriseal NETs in the desired location without guidance-related adverse events.

This study will be an in-hospital study which will follow enrolled subjects for an acute period of up to 48 hours post-placement.

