1 PROTOCOL SUMMARY

1.1 SYNOPSIS

Study Title	A Feasibilty Study to Evaluate the Clinical Safety of Nutriseal™ Nasoenteral Feeding Tube Placement using the Nutriseal™ NUTRIPLACE System in Patients.	
PROTOCOL NUMBER	NUTRI-001	
DEVICE DESCRIPTION	The Nutriseal [™] NUTRIPLACE [™] System is designed to aid qualified operators in the placement of the Nutriseal [™] NasoEnteral Tube [™] of 10 Fr to 12 Fr into the stomach or small intestine of patients requiring enteral feeding. The NUTRIPLACE System is intended as an adjunct to current placement practices for assisting clinical practitioners who place feeding tubes in adult patients.	
	The Nutriseal [™] NasoEnteral Tube has been specifically designed for use with the NUTRIPLACE [™] System and is intended for placement in the stomach or small intestine. It is intended for use in adult patients who require intermittent or continuous feedings via the nasogastric or nasoenteric route.	
Study Objectives	The objective of this study is to assess the safety of the NUTRIPLACE System as an adjunct to current practices for placement of nasoenteral feeding tubes.	
Study Design	The study is a prospective, single center, non-randomized clinical trial in patients that require placement of a nasoenteral feeding tube as a result of their current medical condition.	
Number of Subjects and Sites	Fifty (50) subjects will complete the Procedure Visit (NasoEnteral Tube placement procedure, section 1.3) at a single center by at least five operators. This number (50 subjects) does not include screen failures. Prior to participating in this trial each operator will place a Nutriseal nasoenteral feeding tubes in a run-in patient to provide training on the use of the NUTRIPLACE System.	
DURATION OF PARTICIPATION/STUDY	Each patient's individual participation will last approximately 20-48 hours. It is expected the entire study will take approximately two (2) months to complete.	
STUDY ENDPOINTS	Primary Endpoint:	
	Procedure success: Nasoenteral tube (NET) can be placed in the correct anatomical position without occurrence of guidance-related adverse events.	
	Additional Assessments:	

	Procedure Metrics: Number of placement attempts required				
	Safety: Adverse Events				

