Sample Size Considerations	There is no statistically based sample size for this study which is being conducted to obtain confirmatory evidence to support the safety of using the NUTRIPLACE System as an adjunct to current placement practices for nasoenteral feeding tubes. Fifty (50) patients completing the Procedure Visit (NasoEnteral Tube placement procedure) will provide evidence that the NET tube guidance system does not present new or different safety issues as compared to the predicate (confirmatory study). If less than 45 patients will complete the Follow-up Visit (confirmation of tube tip anatomical location, section 1.3), an enrollment of another 5 patients will be considered.				
SCHEDULED VISITS	This study is an acute safety assessment of the NUTRIPLACE System covering the guidance functionality of the System.				
	Screening The screening visit will occur at time zero and will assess eligibility for the study and obtain informed consent.				
	Procedure The study procedure may occur within two days of screening. Informed consent will affirmed and the patient will be considered enrolled.				
	Final Follow Up The final follow-up visit will occur 20-48 hours following the procedure.				
INCLUSION CRITERIA	 Patients must be ≥21 years of age Patients must require placement of a nasoenteral feeding tube Patients have an endotracheal tube, OR Do not have an endotracheal tube but are sedated and/or classified as obtunded¹ at the time of placement Patients or legal authorized representative must be able to understand and adhere to all protocol procedures and be willing and able to provide written informed consent² 				
Exclusion Criteria	 Patients must not have a history of: Esophageal varices or ulcers Upper airway obstruction Upper GI stenosis or obstruction 				

Obtundation level evaluation is based on Glasgow-Coma scale with a score of between 9 and 12. Sedation level is based on Richmond Agitation-Sedation Scale (RASS) score of -2 or less.
 ² Consent may be provided by patient's legal authorized representative.

	 Trauma involving sinuses, nares face or neck that would prevent NG tube insertion Deformities of the sinus cavities and/or skull base Esophageal cancer or neoplasm Patients must not have a significant concomitant illness that would adversely 			
	affect their participation in the study			
	Female patients who are pregnant or lactating			
STATISTICAL ANALYSIS	All data will be reported using summary statistics.			

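### Adverse-event capture stops at a visit that may fall anywhere from 20 to 48 hours after placement, so patients have no common safety window and the safety conclusion is not tied to one

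*Combined protocol and SAP*

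**What the plan says.** The synopsis (1.1, Scheduled Visits) sets one visit after the procedure: "The final follow-up visit will occur 20-48 hours following the procedure". The flow chart in 1.2 gives the same window and puts study exit directly after it. The synopsis also states: "Each patient's individual participation will last approximately 20-48 hours". Section 4.1 says the study "will follow enrolled subjects for an acute period of up to 48 hours post-placement", which is a ceiling and not a fixed period. The schedule in 1.3 marks AE assessment at the Procedure and Follow-up visits only.

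Section 8.2.4 requires AEs to be documented if they occur while the patient is on study. Follow-up to resolution is required only for serious events already judged related to the system, so nothing looks for new events after exit.

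The primary endpoint (sections 3 and 9.1) combines correct tube position with freedom from guidance-related AEs, and states no time horizon. Section 9.4 plans descriptive summaries, without reference to time observed. The synopsis (Sample Size Considerations) says that 50 patients will give evidence that the guidance system "does not present new or different safety issues as compared to the predicate". The listed risks in 2.3.1 include "pneumonia and sepsis" after placement in the lungs.

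**The concern.** Freedom from guidance-related AEs is half of the primary endpoint, and safety is the only primary objective. If observation ends at a different time in each patient, whether an event counts depends partly on when the visit was booked.

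Take two patients who each develop the same complication at 30 hours. The one visited at 48 hours has a study AE and, if it is judged guidance-related, a failed procedure. The one visited at 20 hours has left the study and counts as a success. The Clinical Events Committee, on which section 6.3 relies to control bias, cannot adjudicate an event that was never recorded.

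The error runs one way: early exit can only remove events, so it can only lower the AE rate and raise the success rate. With 50 patients, each event classed as a failure moves the success rate by 1/50 = 2 percentage points.

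**Working it through.** **Inputs.** Visit window 20 to 48 h (1.1, 1.2, 1.3). N = 50 completing the Procedure Visit (9.2). Pulmonary complications in 0.2% to 1.2% of placements (2.2). The plan gives no figure for observation time to reproduce, and it says that N has no statistical basis.

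**Step 1: spread of observation time.** Longest over shortest = 48/20 = 2.4, a difference of 48 − 20 = 28 h. A patient seen at 20 h is observed for 20/48 = 42% of 48 h. If visits were spread evenly over the window (an assumption), mean observation would be (20 + 48)/2 = 34 h, or 34/48 = 71%. These are shares of hours, not of events.

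**Step 2: what the crude percentage estimates.** Let F(t) be the cumulative incidence of a recordable AE by time t, and tᵢ the exit time of patient i. The planned proportion estimates the average of F(tᵢ), which lies between F(20) and F(48) and refers to no single time. With capture to 48 h in everyone it estimates F(48).

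**Step 3: how many events that could cost.** The documents give no onset times, so onset is assumed here. With exponential onset and mean m hours, the share of eventual events that have appeared by t is 1 − exp(−t/m).

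| Assumed mean onset (h) | By 20 h | By 48 h | Ratio 48 h to 20 h | Visits spread evenly | Evenly spread ÷ by 48 h |
|---|---|---|---|---|---|
| 6 | 0.964 | 1.000 | 1.04 | 0.992 | 0.99 |
| 24 | 0.565 | 0.865 | 1.53 | 0.743 | 0.86 |
| 72 | 0.243 | 0.487 | 2.01 | 0.372 | 0.76 |
| 120 | 0.154 | 0.330 | 2.15 | 0.245 | 0.74 |

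The last column is the fraction of events arising by 48 h that the current plan would record if visits were evenly spread. A record check to 48 h would recover the remainder.

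The result depends on the assumed shape. With log-normal onset (standard deviation 0.5 on the log scale), 20 h against 48 h gives 0.992 against 1.000 for a median of 6 h, 0.358 against 0.917 for 24 h, and 0.040 against 0.500 for 48 h. The steady feature is that visit timing hardly matters for immediate harm and matters a good deal for harm that appears after the first day.

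**Step 4: the numbers at stake.** Expected pulmonary complications in 50 patients are 50 × 0.002 = 0.1 to 50 × 0.012 = 0.6. The chance of at least one with complete capture is 1 − 0.998⁵⁰ = 9.5% to 1 − 0.988⁵⁰ = 45%. At the 1.2% rate with assumed exponential onset of mean 72 h, it is 25% if every patient is observed to 48 h and 14% if every patient leaves at 20 h. At 0.2% the two figures are 4.8% and 2.4%.

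Zero events in 50 would give a one-sided 95% upper limit of 1 − 0.05^(1/50) = 5.8%, and only for events arising within the time actually observed.

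**The case against.** The strongest defence is scope. The synopsis calls the study an acute assessment of guidance function, and 4.1 speaks of safety during placement. A short window is therefore a declared choice. That stands, but it defends a short window. It does not defend one that varies by patient, or a conclusion with no time attached.

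The second defence is that the main route to pulmonary harm is caught early. Every patient has AEs assessed at the Procedure Visit and an X-ray within five hours (1.3), so a tube left in the lung fails the position half of the endpoint at once. This also stands, and it narrows the point considerably. What remains is harm that appears later, for example after a brief airway entry corrected before the film. Section 2.2 describes that kind of correction as the system's benefit.

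Third, with 0.1 to 0.6 expected pulmonary events, 55% to 90% of such studies would see none even with perfect capture. That is true: sample size limits the safety evidence more than the window does.

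Fourth, the study is single-arm and descriptive, with no hypothesis and no subgroups, so unequal observation distorts no planned comparison. That is also true, but the AE and success percentages remain affected.

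A reader might infer three stronger claims that the documents do not support:
- **That observation does differ 2.4-fold.** This is only the maximum the window allows. Nor is there any evidence that the site would book visits early to avoid events.
- **That the protocol's own risk list shows harms developing over days.** Section 2.3.1 gives a time course for one item only: "Damage to nasal ciliary epithelium leading to infection and/or sinusitis following long-term presence of an nasoenteral tube". That harm comes from tube dwell and falls largely outside a guidance endpoint. Later onset of pneumonia or sepsis is plausible but not stated.
- **That a longer review, say to day 7, is required.** No such horizon follows from the documents. In intubated, sedated or obtunded patients without a control group, it would add background events that are hard to attribute.

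**Conclusion.** The point holds as a modest and cheaply corrected weakness. The plan sets no common AE horizon, allows up to a 2.4-fold difference in observation, and does not limit its safety conclusion to the time observed. Any resulting error favours the device.

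Its size is uncertain. For harm that appears within hours the loss is about 1%. With visits spread evenly and mean onset of one to five days, about 14% to 26% of the events arising by 48 h would be missed under exponential onset. Those figures rest on assumed onset and visit times, which the documents do not give. In absolute terms few events are expected in 50 patients, so the likely effect is none or one event, worth 0 or 2 percentage points on the success rate. The conclusion also rests on reading exit as occurring at the follow-up visit, which is how the flow chart in 1.2 and the stated duration in 1.1 present it.

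**What to change.** Keep the X-ray visit at 20 to 48 hours. In 1.3, 4.1 and 8.2.4, state one AE window: all AEs to a full 48 hours after placement for every patient, obtained by a hospital-record check when the visit takes place earlier. Send events found this way through the same relatedness and guidance categories (8.2.3.2) and the same committee review. Align the duration wording in 1.1. Word the safety conclusion in 1.1 as applying to acute events within 48 hours of placement only.

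This brings the ratio of observation times from a possible 2.4 down to 1.0. The cost is a short chart check by existing site staff on patients who are expected to be in hospital, minor protocol and consent wording, and a possibly slightly less favourable AE rate. No visit, film or test is added. A longer record review is an option for the sponsor to weigh, not part of this change.
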